If the Enrollment Visit 3 (Day 1) is scheduled to occur beyond four (4) weeks (>28 days) for Cohort 1 or beyond six (6) weeks (>42 days) for Cohort 2 from the occurrence of Screening Visit 1, sites must contact the Sponsor before proceeding. Depending on the expected duration of the delay in conducting Visit 3, an Unscheduled Visit may be required to repeat certain screening procedures.

The overall Screening Period may be accelerated in Cohort 1 to less than two (2) weeks total if all visit procedures and results are completed and confirm the subject's eligibility for the trial. For Cohort 2, a minimum of two weeks must elapse between Visit 2 and Visit 3.

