7.12. Blood Glucose Monitoring – Cohort 2 Only

Throughout the trial in both Cohorts, the exogenous insulin requirements of enrolled subjects are managed and titrated by the Investigator (or qualified designee) as needed to maintain glycemic control in conjunction with standards of care. For purposes of this study, in Cohort 2, the diary entries made by the subjects (e.g., insulin doses, SMBG values, and HE occurrences) are the main sources of information available to the Investigator to assist with treatment decisions. CGM data may be utilized for treatment decisions in accordance with local labeling market approvals.

In addition to Investigator review of glucose trends, insulin dosing, and HE occurrences, the Sponsor will conduct routine reviews of blood glucose data. These data are collected as part of the required study procedures. Subjects record insulin dosing and all HE occurrences on a study diary and glucometer data are electronically downloaded. The data are then available in near real-time for review. If potentially concerning trends are evidenced for an

individual subject, the Sponsor will notify the Investigator and request for follow-up with the subject to occur if necessary.

Blood glucose monitoring is performed through various methods throughout Cohort 2 of this study to ensure proper glucose control:

- Laboratory tests (Section 7.17)
- Continuous Glucose Monitoring (Section 7.14)
- Self-Monitoring Blood Glucose (Section 7.15)

Data from these methods will be available to the Investigator via reports from laboratories, study diaries, and downloads or entries from CGM and SMBG meters to facilitate treatment decisions. The glucose monitoring data collected in Cohort 2 between Visit 2 (Week -4) and Visit 3 (Day 1) establishes the baseline profile of each subject's glycemic control (e.g., the percent time spent at various blood glucose cutoff points per CGM data, SMBG blood glucose levels, exogenous insulin doses, and frequency of HEs).

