10. STATISTICAL CONSIDERATIONS

Methodology for the summarization and analysis of the data collected in this trial are given here and further detailed in a Statistical Analysis Plan (SAP), which will be maintained by the Sponsor. If the DSMB is requested to review the data from Cohort 1, the study SAP will be written and approved prior to the Cohort 1 data cut-off (e.g., the data through Week 4 for the final subject in Cohort 1 whose data is part of the DSMB data review).

The study SAP may modify what is outlined in the protocol; however, any major modifications of the endpoints or their analyses will be reflected in a protocol amendment.

The phrase "treatment group" is used in this section to denote the number of initially implanted sentinel units in Cohort 1 or initially implanted VC-01-DF dose-finding units in Cohort 2. In Cohort 1, if a subject has a sentinel unit explanted for any reason and remains in the study, then he/she will be included in the treatment group that is described by the number of sentinel units originally implanted. For Cohort 2, if a subject has a VC-01-DF unit explanted for any reason and remains in the study, then she/he will be included in the treatment group that is described by the number of VC-01-DF units originally implanted. If a Cohort 2 subject has no VC-01-DF units implanted, but has sentinel units implanted, then the subject will be included in the "0 implanted VC-01-DF units" treatment group for Cohort 2. If, during the course of the study, further enumeration is needed to differentiate treatment group (for example, if it is necessary to differentiate multiple EDDS configurations used in Cohort 1), then that further detail will be included in the study SAP.

Where appropriate, data from subjects in Cohort 1 and in Cohort 2 will be summarized together (within the same table). When data from the two cohorts is included in the same table, the treatment group will be used to differentiate the data from Cohort 1 and Cohort 2.

[figure not shown]

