## 7.2 Baseline, Endpoint and Missing Value Definitions

#### 7.2.1 Baseline

Baseline will be defined as the last non-missing value prior to the start time of the surgical implantation procedure unless otherwise specified. For MMTTs in Cohort 2 subjects, the 4-hour MMTT performed during the Screening period is used for defining both the baseline 4-hour MMTT and the baseline 2-hour (using the first 2 hours of data) MMTT.

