## 7.2.6.3.1 Daily and Weekly Exogenous Insulin Dose

For subjects in Cohort 2, baseline average daily and average weekly exogenous insulin dose requirements will be calculated using up to 28 days of data. Baseline average daily and average weekly insulin requirements will be calculated using data starting at Day -1 (the day prior to implant) and working backwards for up to 28 days (through Day -28). For instances in which the available pre-implant data provides less than 28 days of data, post-implant data will be used to supplement, using Day 4 forward until 28 days of data are available. Data from days on which an MMTT or SOGCT was performed, will not be included in the calculation.

At Weeks 16, 20, 26, 39 and 52, the last 7 daily total exogenous insulin doses recorded in the log will be used to calculate the average daily and weekly exogenous insulin dose at that visit. The last 7 daily records must be within the previous 14 calendar days and may not include a day in which an MMTT or SOGCT was performed. There must be at least 4 different days worth of data for a particular timepoint to be considered evaluable.

The weekly average value will be calculated as:

7 \* (sum of the insulin doses during the period / number of days with insulin doses in the period).

The percent reduction in average weekly exogenous insulin dose from baseline at these visits will be calculated as:

(Average weekly insulin dose at post-baseline visit - baseline average weekly insulin dose)\*100/ baseline average weekly insulin dose.

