## 7.2.6.4 Percent of Time Spent with Blood Glucose Values at Various Cut Points

Cohort 2 subjects will be provided with a CGM system by the Sponsor and are required to use the Sponsor-provided CGM during study participation. The blood glucose value cut points of <54 mg/dL,  $\geq$ 54 to <70 mg/dL,  $\geq$ 70 mg/dL to  $\leq$ 180 mg/dL,  $\geq$ 180 mg/dL and >250 mg/dL will be assessed.

The assessment of blood glucose cut points will be performed three ways: over the entire 24-hour time period, over the nocturnal (CGM value below/above the cut point occurs between 12 a.m. - 6 a.m.) time period, and over the daytime (CGM value below/above the cut point occurs between 6 a.m. - 12 a.m.) time period.

Baseline CGM data will be utilized to calculate percentages of time spent with blood glucose values at the various cut points for up to 28 days, starting at Day -1 (i.e., the day prior to implant) and working backwards for up to 28 days (through Day -28). For instances in which the available pre-implant data provides less than 28 days of data, post-implant data will be used, from Day 4 forward until 28 days of data are available. In addition, the CGM data from the 14 days prior to each scheduled clinic visit will be used to calculate percentages spent with blood glucose values at the various cut points for these visits. For all timepoints (baseline and on-study), data should not be used if an SOGCT (baseline only) or MMTT was performed on that day.

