## 7.2.6.5 Frequency of HEs using Subject-Reported Diary Data

HE data collected from the subject-completed diaries will be used for assessment of efficacy. Investigators will review the HE logs in the diary at each study visit. Blank values in the HE log are considered to be 0 values.

HEs will be classified in six ways: total HEs, severe HEs (SHEs), nocturnal HEs, severe nocturnal HEs, daytime HEs, and severe daytime HEs. Total HEs are HEs that occur at any time during the 24-hour period; SHEs are HEs requiring the aid of another person to administer carbohydrates, glucagon, or other resuscitative assistance any time during the 24-hour period. Nocturnal HEs are HEs that start during the 12 a.m. -6 a.m. period; severe nocturnal HEs are SHEs that start during the 12 a.m. -6 a.m. period. Daytime HEs are HEs that start during the 6 a.m. -12 a.m. period; severe daytime HEs are SHEs that start during the 6 a.m. -12 a.m. period.

The baseline average weekly frequency of subject-reported HEs, SHEs, nocturnal HEs, severe nocturnal HEs, daytime HEs and severe daytime HEs will be calculated using up to 28 days of data. The baseline average weekly frequency will be calculated using data starting at Day -1 (i.e., the day prior to implantation) and working backwards for up to 28 days (through Day -28). For instances in which the available pre-implant data provides less than 28 days of data, post-implant data will be used from Day 4 forward until 28 days of data are available. Data from days on which the Screening SOGCT or the MMTT was performed will not be used in the calculation.

The total number of HEs, SHEs, nocturnal HEs, severe nocturnal HEs, daytime HEs, and severe daytime HEs occurring in the 14 days prior to each specified time point (Weeks 16, 20, 26, 39, and 52) will be used to calculate the weekly frequency of total HEs, SHEs, nocturnal HEs, severe nocturnal HEs, daytime HEs, and severe daytime HEs, respectively, at the specified time point. Data for HEs/SHEs should not be used if an MMTT was performed on that day.

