## 7.2.6.6 Frequency of HEs using CGM Data

CGM will be utilized, based on the below specified rules, to evaluate the number of hypoglycemic episodes (number of times blood glucose falls below 70 mg/dL) and the number of severe hypoglycemic events (number of times blood glucose falls below 54 mg/dL) for each subject:

- A set of CGM readings < 70 mg/dL or <54 mg/dL, with a minimum overall duration of 15 minutes
- Up to two consecutive readings >= 70 mg/dL (or >= 54 mg/dL for separate summary) are allowed within the same episode
- If a subsequent episode starts within 60 minutes of the start of the previous episode, then they are combined and counted only as one episode

The total number (over the entire 24-hour time period) of episodes will be calculated as well as the number of nocturnal (starts during the 12 a.m. - 6 a.m. period) episodes and the number of daytime (starts during the 6 a.m. to 12 a.m.) episodes.

Baseline CGM-reported HE data will be calculated using up to 28 days of data. Baseline CGM-reported HEs will be recorded starting at Day -1 (i.e., the day prior to implant) and working backwards for up to 28 days (through Day -28). For instances in which the available pre-implant data provides less than 28 days of data, post-implant data will be used from Day 4 forward until 28 days of data are available. These data will be used to calculate the baseline number of weekly total episodes, weekly nocturnal episodes, and weekly daytime episodes. In addition, the CGM data from the 14 days prior to each scheduled clinic visit will be used to calculate the number of weekly total episodes, the number of weekly nocturnal episodes, and the number of weekly daytime episodes for each of these visits. For baseline and on-study time points, data from days on which an SOGCT (baseline only) or MMTT was performed should not be used.

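### The SAP fills a short pre-implant baseline for insulin, CGM and hypoglycaemia with days after implant and sets no limit on their share: 0–4% on the nominal schedule, about half at the two-week screening minimum

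*SAP*

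**What the plan says.** SAP 7.2.6.3.1 averages insulin dose over Day -1 back to Day -28. If that yields fewer than 28 days, "post-implant data will be used to supplement, using Day 4 forward until 28 days of data are available". The rule recurs for CGM cut points in 7.2.6.4 ("post-implant data will be used, from Day 4 forward until 28 days of data are available"), diary HEs in 7.2.6.5 ("post-implant data will be used from Day 4 forward until 28 days of data are available") and CGM-derived HEs in 7.2.6.6 ("For instances in which the available pre-implant data provides less than 28 days of data, post-implant data will be used from Day 4 forward"). Days with an MMTT or SOGCT are left out.

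The total is capped at 28 days. Nothing caps the post-implant part, fixes a last day for it, or requires any pre-implant days. The only day-count minimum, four days in 7.2.6.3.1, stands in the paragraph on Weeks 16 to 52. Even if applied to baseline, it would not require those days to precede implant.

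Protocol 7.12 states: "The glucose monitoring data collected in Cohort 2 between Visit 2 (Week -4) and Visit 3 (Day 1) establishes the baseline profile". It lists time at CGM cut points, insulin doses and HE frequency among the contents and mentions no days after implant.

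Three further provisions bear on the point:

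- SAP 7.2.1: "Baseline will be defined as the last non-missing value prior to the start time of the surgical implantation procedure unless otherwise specified".
- Protocol section 10: "The study SAP may modify what is outlined in the protocol", with major changes to endpoints or analyses to go into an amendment.
- Protocol 6.2: "For Cohort 2, a minimum of two weeks must elapse between Visit 2 and Visit 3".

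**The concern.** Cohort 2 has no untreated arm. Baseline is therefore each subject's own reference for change in insulin dose, the 50%-reduction rate, time in range and HE frequency at Weeks 16 to 52. It is also the covariate in the ANCOVAs of SAP 7.3.7.3. Under the top-up rule the content of that reference varies with the length of screening, and for a briefly screened subject it can consist largely of days after surgery.

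The protocol gives two reasons why those days might differ from pre-implant days. Activity is restricted for a week after implant (5.4.2). The investigator also reviews the diary at every visit to decide on insulin changes (7.13); Visit 4 (Day 2) falls just before the top-up days and Visit 5 (Week 2) can fall among them.

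**Working it through.** **Inputs.** The baseline window is Day -28 to Day -1. There is no Day 0, because the SAP calls the day before implant Day -1, so the window holds 28 days, as the SAP says. Diary and CGM start at Visit 2 (protocol 6.2), the same visit as the baseline 4-hour MMTT, so the Visit 2 day is excluded if it lies in the window. Visit 2 has target Day -28 and SAP window Day -31 to Day -1 (SAP 7.2.2). Two weeks before Day 1 is Day -14.

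**Share with complete data.** With Visit 2 on Day -g, usable pre-implant days are u = 28 if g ≥ 29, otherwise g − 1. Top-up days are n = 28 − u, taken from Day 4 to Day 3 + n. The share is n/28. The alternative reading assembles 28 calendar days first and then drops the MMTT day.

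| Visit 2 | u | n (days used) | n/28 | Alternative reading |
|---|---|---|---|---|
| Day -29 or earlier | 28 | 0 | 0% | 0% |
| Day -28 | 27 | 1 (Day 4) | 3.6% | 0/27 = 0% |
| Day -21 | 20 | 8 (Days 4–11) | 28.6% | 7/27 = 25.9% |
| Day -15 | 14 | 14 (Days 4–17) | 50.0% | 13/27 = 48.1% |
| Day -14 | 13 | 15 (Days 4–18) | 53.6% | 14/27 = 51.9% |

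**Gaps.** The documents give no CGM capture rate. If a fraction c of pre-implant days is captured, the share is (28 − c·u)/28. An assumed c of 0.8 to 1.0 gives 0–20% at Day -29 or earlier, 4–23% at Day -28, 29–43% at Day -21 and 54–63% at Day -14. Diary gaps should be smaller, because daily entry between Visits 2 and 3 is a condition of eligibility (protocol 6.2) and is checked at Visit 3 (6.3).

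**Illustration on insulin (assumed ±10% shift, not from the documents).** Let the dose on the top-up days differ by d from the pre-implant dose, and let s be the share. The baseline is multiplied by 1 + s·d. A subject with no true effect shows a change of 1/(1 + s·d) − 1, and the 50% criterion is met at a true reduction of 1 − 0.5(1 + s·d).

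- s = 15/28, d = +10%: apparent change −5.1%, criterion met at 47.3%.
- s = 15/28, d = −10%: apparent change +5.7%, criterion met at 52.7%.
- Shift confined to Days 4–8 of the activity limit (s = 5/28): about −1.8% or +1.8%, criterion met at 49.1% or 50.9%.
- s = 1/28: about 0.4% either way.

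**Overlap with follow-up.** The earliest Week 16 day in the SAP window is Day 100, so its 14-day look-back starts on Day 86. With no pre-implant days at all and complete data afterwards, the top-up ends on Day 31. The overlap at Week 16 and later is therefore 0 days. Descriptive CGM summaries at early visits can share days. For Visit 2 on Day -14 (top-up Days 4–18) and visits on target, the Week 2 window (Days 1–14) shares 11 days with baseline and the Week 4 window (Days 15–28) shares 4.

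**Precision given up without the top-up.** With b baseline days, f follow-up days and independent days, the error SD of the change relative to 28 baseline days is √[(1/b + 1/f)/(1/28 + 1/f)].

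- b = 13: √(0.2198/0.1786) = 1.11 for insulin (f = 7); √(0.1484/0.1071) = 1.18 for CGM and HEs (f = 14).
- b = 27: 1.004 and 1.006.
- b = 4: 1.48 for insulin.

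**The case against.** The best defence is that this is a deliberate, prespecified choice that trades a little purity for a fuller baseline, stated alike in four sections. Starting at Day 4 skips the day of surgery and the two days after it. Subjects must have had a stable, optimised regimen for at least three months (inclusion criterion 4), so an abrupt dose shift is not to be expected. Visit 2 is planned for Week -4, where almost nothing is added, and the documents do not show how many subjects, if any, are screened in two weeks. A shift common to all groups would largely cancel in the between-group comparisons unless screening length differed by group. The secondary p-values are declared descriptive.

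Most of this stands, and it limits the point. It does not remove it. Within-group changes and the 50%-reduction rate remain exposed. The precision argument is weak: the SAP accepts 7 insulin days (at least 4) and 14 CGM or HE days at follow-up, so 13 pre-implant days is not an unusually thin basis.

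Three stronger readings are tempting and are not supported:

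- *The SAP breaches the protocol.* Protocol 7.12 does not say that only Visit 2 to Visit 3 may be used, and both SAP 7.2.1 and protocol section 10 leave room for a different rule.
- *The graft's own effect leaks into baseline.* The protocol describes the islet-equivalent dose at implant as negligible (5.1.4.1) and expects insulin reduction over three to six months (7.12), so an effect by Day 18 is unlikely.
- *The secondary results are biased.* The activity limit and the dose reviews give neither a size nor a direction, and the ±10% shift above is an assumption.

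**Conclusion.** The point holds as a departure to reconcile and a cheap improvement. The four SAP sections let the post-implant part of baseline grow without limit, and a schedule the protocol permits makes it about half: 52–54% with Visit 2 on Day -14, depending on when the MMTT day is dropped, and 50% on Day -15 under the plain reading. On the nominal schedule it is 0–4%. These figures assume complete data; CGM gaps raise them.

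The affected quantities are the secondary insulin, CGM and HE endpoints. The primary C-peptide endpoint and insulin independence do not use this baseline, and the Week 16 to 52 windows never share days with it. What is established is that the reference depends on screening length and can contain post-operative days. Whether that moves any result is open.

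**What to change.** In SAP 7.2.6.3.1, 7.2.6.4, 7.2.6.5 and 7.2.6.6, replace the supplement sentence so that the main baseline is all available days from the later of Visit 2 and Day -28 through Day -1, without MMTT or SOGCT days and without post-implant data. Then:

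- **Insulin:** apply the existing four-day minimum to baseline. Do not carry it over to the other measures, for which the SAP sets none.
- **Diary HEs:** count days from the dispensing of the diary at Visit 2. Section 7.2.6.5 reads blanks as zero, so days before dispensing would otherwise count as event-free.
- **CGM:** use the days with CGM data.
- **Topped-up 28-day baseline:** keep it as a sensitivity analysis, and for any subject with no usable pre-implant data (for insulin, fewer than four days), who would otherwise have no baseline. Flag such subjects, and state whether the MMTT day is dropped before or after the 28 days are counted.
- **Reporting:** give the number of post-implant days used per subject.

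This moves the SAP towards protocol 7.12 and needs no protocol amendment; the existing Day -28 limit stays. The cost is SAP wording and one additional run. Short-screened subjects get a noisier baseline: about 11% (insulin) or 18% (CGM, HEs) more day-to-day error SD in the change at 13 days, under 1% on the nominal schedule, and about 48% for an insulin baseline at the four-day floor.

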## **Efficacy**

- Change from baseline to Weeks 8, 12, 16, 20, and 39 in C-peptide  $AUC_{0-2h}$  and change from baseline to Week 52 in C-peptide  $AUC_{0-4h}$  following an MMTT.
- Change from baseline to Weeks 16, 20, 26, 39 and 52 in average daily insulin dose.
- Time to onset of biological response of C-peptide following MMTT.
- Percent of subjects achieving a positive stimulated C-peptide (defined as > 0.2 ng/mL) after implant
- Percent of subjects who achieve a 50% reduction in average weekly exogenous insulin dose from baseline to Weeks 16, 20, 26, 39, and 52.
- Percent of subjects who achieve exogenous insulin independence; of those subjects achieving insulin independence, the percent achieving HbA1c < 7.0%.

- Percent of time spent with blood glucose values at various cut points (e.g., <54 mg/dL, ≥54 to < 70 mg/dL, ≥70 mg/dL to ≤180 mg/dL, >180 mg/dL and >250 mg/dL) as measured by each subject's CGM.
- Change from baseline to Weeks 16, 20, 26, 39 and 52 in time-in-euglycemic range (≥70 mg/dL to ≤180 mg/dL), time-in-hypoglycemic ranges (<54 mg/dL and ≥54 to <70 mg/dL), and time-in-hyperglycemic ranges (>180 mg/dL and >250 mg/dL) as measured by each subject's CGM.
- Change from baseline to Weeks 16, 20, 26, 39, and 52 in weekly frequency of hypoglycemic events;
- Change from baseline in frequency of hypoglycemic events (24-hour; daytime [start between 6a.m.-12a.m.]; nocturnal [start between 12a.m.-6a.m.]) to Weeks 16, 20, 26, 39 and 52.
- Percent of subjects free of severe hypoglycemic events between study visits starting with Week 16 (i.e., Weeks 16-20, Weeks 20-26, Weeks 26-39, Weeks 39-52/ET, and Weeks 16-52/ET).

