## 7.1 Statistical Power and Sample Size Considerations

There are no statistical hypotheses being tested.

In Cohort 1, up to 30 subjects will be enrolled. In Cohort 2, up to 40 subjects will be enrolled, for a total enrollment of up to 70 subjects in both cohorts.

The sample size in Cohort 1 was empirically derived, based upon safety considerations and data accumulated from other previously performed ViaCyte clinical trials. A sample size of up to 30 subjects should allow for adequate assessment of Cohort 1 study objectives.

A sample size of 40 subjects in Cohort 2	
u u	
	Since Cohort 1 has the primary objective of
evaluating initial safety and tolerability, the	ese subjects will not contribute MMTT data
for the Week 26 analysis.	

For the 2-hour MMTT, a sample size of 40 subjects will

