## 7.2.5 Change From Baseline

Change from baseline is defined as:

Value of parameter post-baseline – Value of parameter at baseline

If the post-baseline value for a specific parameter at a specific timepoint is missing, then the change from baseline at that timepoint will not be calculated. The subject will not be included in the change from baseline at that timepoint, for that parameter (but will be included in the change from baseline for other timepoints where the subject has post-baseline data for that same parameter).

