## 7.3.7.3 Cohort 2 Secondary Efficacy Analyses

Each of the secondary efficacy endpoints will be analyzed using an  $\alpha = 0.05$  level of significance. Given the large number of secondary efficacy endpoints, the p-values for these endpoints will be considered descriptive.

The FAS will be used to analyze the secondary efficacy endpoints, with the analysis for each endpoint performed within Cohort 2 subjects only. Change from baseline to Weeks 16, 20, 26 and 39 in C-peptide AUC0-2h following an MMTT and change from baseline to Week 52 in C-peptide AUC0-4h following an MMTT; change from baseline to Weeks 16, 20, 26, 39 and 52 in average daily insulin dose in the seven days preceding the clinic visit; and change from baseline to Weeks 16, 20, 26, 39 and 52 in time in euglycemic range, time in hypoglycemic range, and time in hyperglycemic range will each be analyzed using ANCOVA, with treatment group as a factor and the relevant baseline as a covariate.

Time to onset of biological response of C-peptide following an MMTT will be assessed using Kaplan-Meier curves, with the p-value from the logrank test also provided.

The percent of subjects who achieve a positive stimulated C-peptide (defined as > 0.2 ng/mL) after implant; the percent of subjects who achieve a 50% reduction in average weekly exogenous insulin dose from baseline to Weeks 16, 20, 26, 39 and 52; and the percent of subjects who achieve exogenous insulin independence, percent of subjects (of those achieving insulin independence) achieving  $HbA1c \le 7.0\%$  will each be analyzed using Fisher's exact test. The number and percent of subjects in each treatment group and the p-value from the Fisher's test will be provided (at each timepoint, where appropriate).

The percent of time spent with blood glucose values at various cut points as measured by each subject's CGM will be summarized descriptively. The percentages and change from baseline percentages will be summarized for each cut point (<54 mg/dL,  $\ge54$  to <70 mg/dL,  $\ge70$  mg/dL to  $\le180$  mg/dL, >180 mg/dL and >250 mg/dL) and for each treatment group.

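### SAP 7.2.6.3.1 computes the insulin percent reduction as post-baseline minus baseline, so a halved dose scores −50 and a 50% increase scores +50; read literally, the 50%-reduction responder endpoint is reversed

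*SAP*

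**What the plan says.** SAP 7.2.6.3.1 sets out how the weekly insulin dose is derived for Cohort 2 and then states: "The percent reduction in average weekly exogenous insulin dose from baseline at these visits will be calculated as". The numerator that follows is "Average weekly insulin dose at post-baseline visit - baseline average weekly insulin dose", multiplied by 100 and divided by the baseline average weekly dose.

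The endpoint that needs this quantity is listed in SAP 4.2 under Efficacy: "Percent of subjects who achieve a 50% reduction in average weekly exogenous insulin dose from baseline to Weeks 16, 20, 26, 39, and 52". The protocol lists the same endpoint in its summary and in section 2.2.2. For the analysis, SAP 7.3.7.3 refers to "the percent of subjects who achieve a 50% reduction in average weekly exogenous insulin dose from baseline" and assigns Fisher's exact test, reported by treatment group. Protocol 10.4.4.2.2 does the same.

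None of these places gives a numerical cut-off with a sign, uses an absolute value, or says whether a fall of exactly 50% counts as a response.

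SAP 7.2.5 gives the general definition of change from baseline as "Value of parameter post-baseline – Value of parameter at baseline". This is the same direction of subtraction as in 7.2.6.3.1, but there it is called change.

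**The concern.** The name and the formula disagree in sign. A percent reduction should be positive when the dose falls; the printed expression is negative when the dose falls and positive when it rises. The endpoint asks who achieved a 50% reduction, and the only variable the SAP supplies under that name runs the opposite way. Comparing that variable with 50 gives a responder flag for the wrong subjects.

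Reduced exogenous insulin is one of the potential benefits that protocol 1.4.2.2 lists for Cohort 2, and this endpoint is reported at five time points. A derivation formula is what the programmer codes from and what the validator checks against. If both follow the text, independent programming would agree on the wrong answer. Even with a sensibly coded flag, a table of percent reduction would show negative numbers for subjects who improved.

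**Working it through.** **Inputs.** The formula comes from SAP 7.2.6.3.1 and the responder definition, in words only, from SAP 4.2 and 7.3.7.3. The plan prints no numerical result on this point, so there is no figure to reproduce. The baseline of 280 units/week below is an assumption for illustration.

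**General form.** Let the post-baseline weekly dose be f × baseline, with f ≥ 0.

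- SAP formula: (f × baseline − baseline) × 100 / baseline = 100 × (f − 1).
- A percent reduction in the ordinary sense: (baseline − f × baseline) × 100 / baseline = 100 × (1 − f).

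One is the negative of the other, and the baseline cancels. A fall of at least half means f ≤ 0.5, where the SAP value lies between −100 and −50. An SAP value of at least +50 requires f ≥ 1.5, a dose increase of half or more. The two sets do not overlap, so a +50 cut on the printed formula captures no true responder at all.

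**With numbers, baseline 280 units/week.**

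| Post-baseline dose (units/week) | SAP formula | Flag if SAP value ≥ 50 | Baseline minus post | Flag if ≥ 50 | Flag if SAP value ≤ −50 |
|---|---|---|---|---|---|
| 0 (no insulin) | (0 − 280) × 100 / 280 = −100 | no | +100 | yes | yes |
| 70 | (70 − 280) × 100 / 280 = −75 | no | +75 | yes | yes |
| 140 (halved) | (140 − 280) × 100 / 280 = −50 | no | +50 | yes | yes |
| 142.8 (49% lower) | (142.8 − 280) × 100 / 280 = −49 | no | +49 | no | no |
| 280 (unchanged) | 0 | no | 0 | no | no |
| 420 (50% higher) | (420 − 280) × 100 / 280 = +50 | yes | −50 | no | no |
| 560 (doubled) | (560 − 280) × 100 / 280 = +100 | yes | −100 | no | no |

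The third column is the literal reading of the SAP. It counts the subjects at 420 and 560 units and misses those at 0, 70 and 140. The last two columns are the two possible corrections, and they agree in every row.

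**The case against.** The strongest reply is that the SAP never prints a +50 cut-off. It describes the endpoint in words, and anyone who computes the value and then looks for subjects whose dose fell by half will find them at or below −50. On this view the formula follows the convention of SAP 7.2.5, the slip is only the word reduction, and the intended meaning is plain. An error would also be easy to notice: a subject on no insulin would score −100 and be called a non-responder, which would contradict both the insulin-independence endpoint and the change in average daily dose. Both come from the same insulin logs without this formula.

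The stakes are also limited. This is one of many secondary endpoints, SAP 7.3.7.3 treats their p-values as descriptive, and SAP 7.1 states: "There are no statistical hypotheses being tested".

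Much of this stands as a limit on severity. The reversal is conditional on comparing the named variable with +50, and an alert programmer would avoid it. It does not rescue the text. To reach the right answer, the programmer must either disregard the variable's name or supply a negative cut-off that neither document contains. That the error might be caught later is no reason to leave it in the derivation rule.

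**Conclusion.** The point holds. The formula in SAP 7.2.6.3.1 is a percent change labelled as a percent reduction, and nothing elsewhere in the SAP or protocol corrects the sign.

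Under the literal reading, with the named variable compared with +50, misclassification of true responders is complete at each of the five visits, and subjects whose insulin rose by half or more are counted instead. This does not depend on the assumed baseline dose. It does depend on the +50 reading, which the plan implies by its wording but does not print.

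The effect is confined to one secondary responder endpoint and any display of percent reduction. The primary C-peptide endpoint, the ANCOVA of average daily insulin dose and both definitions of insulin independence are untouched. The formula should be corrected, but the error does not threaten the main conclusions of the trial.

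**What to change.** In SAP 7.2.6.3.1, replace the formula with (baseline average weekly dose − post-baseline average weekly dose) × 100 / baseline average weekly dose, and define a responder as a subject with a value ≥ 50.

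An equally good alternative keeps the formula, renames the quantity percent change, in line with SAP 7.2.5, and defines a responder as a value ≤ −50. Either version also settles that a fall of exactly 50% counts, which the documents leave unstated.

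The cost is one line in the SAP. It needs no new data and changes no clinical procedure. It should be done before database lock, so that the sign and cut-off are not chosen after the open-label results are known.
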